-----------------------------	---

	
adequately resected carcinoma in situ (e.g. cervix) may enroll irrespective of the time of diagnosis.
 
 4. Prior exposure to azacitidine, decitabine or investigational hypomethylating agent or induction chemotherapy for MDS or AML. Note: intensive chemotherapy for any other prior cancer is not exclusionary. 5. Use of cytotoxic chemotherapeutic agents, or experimental agents (agents that are not commercially available) for the treatment of MDS within 14 days of the first day of study drug treatment. 6. Concurrent use of erythroid stimulating agents, G-CSF, or GM-CSF within 14 days of the first day of study drug treatment. 7. History of allogeneic stem cell transplantation 8. Pregnancy: Pregnant women are excluded from this study because APR-246 has not been studied in pregnant patients. Because there is an unknown but potential risk for adverse events in nursing infants secondary to treatment of the mother with APR-246, breastfeeding should be discontinued if the mother is treated with APR-246. 9. Active uncontrolled infection.

Treatment plan
	
Treatment will be administered on an outpatient basis. No investigational or commercial agents or therapies other than those described below may be administered with the intent to treat the patient's disease.
 
Patients will be randomized (1:1) to 1 of 2 arms and stratified by age (<65 versus ≥65):
 
 1) Experimental: APR-246 + azacitidine; or 2) Control: azacitidine only 
Treatment Schedule for Experimental Arm: APR-246 + Azacitidine
 
  
 
APR-246 will be administered as a 6-hour intravenous (IV) infusion daily on days 1-4 of each 28-day cycle. APR-246 fixed dose is 4.5 g. One dose level reduction to 4.0 g is permitted. A second dose reduction could be permitted following discussion with the Sponsor and Medical Monitor.
 
Azacitidine will be given at the standard dose of 75 mg/m² over 7 consecutive days (Days 4-10) as a subcutaneous injection or IV infusion, every 28 days.
 
Control arm: Azacitidine (75 mg/m²) only, on Days 4-10, as a subcutaneous injection or IV infusion, every 28 days.

Dose delay / modifications
	
Dose delays/modifications are permitted per protocol. A single missed dose may be compensated by adding an additional dosing day for azacitidine, so that the patient

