6.0 TREATMENT OF SUBJECTS

6.1 Drug Preparation and Administration

At the pharmacies, the IMP vials are to be stored at 2-8°C (35.6-46.4°F). At the pharmacies and at the study centers, the prepared APR-246 study product (diluted in sodium chloride solution) is to be stored at not more than 25°C. The infusion should be completed within 24 hours from the time of preparation (see Pharmacy Binder).

APR-246 treatment (Experimental Arm only) will be administered on Days 1-4, and azacitidine on Days **4-10** (Figure 4). Treatment may be administered on an outpatient basis. No investigational or commercial agents or therapies other than those described below may be administered with the intent to treat the patient's disease.

Patients will be randomized (1:1) to 1 of 2 arms, Experimental or Control arm.

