7.4 Control Arm (azacitidine)

In the event that a visit or test cannot be scheduled on the exact visit day, a window of ±3 days is allowable. After the first cycle, Day 1 of each subsequent cycle is the same as Day 29 of the previous cycle.

7.4.1 Each Cycle Day 1 \pm 3 Days (same as Day 29 of previous cycle) through Day 10

Tests should be performed prior to first dose

Day 1 examinations marked * do not need to be repeated if already performed within 3 days prior to day 1 cycle 1.

- Adverse Events: All adverse events since the last visit should be recorded. Even though pre-medicated, patients should be closely monitored.
- Concomitant medications.
- Physical examination: Day 1*. Weight, body surface area.
- ECOG performance status: Day 1.
- Vital signs. **If azacitidine is given IV:** before (within 0-2 hours) and EOI (30-60 minutes). **If azacitidine is given SC: before administration (within 0-2 hours).**
- Hematology: Day 1* hemoglobin, hematocrit, MCV, platelet count, blasts, WBC and WBC differentials.
- Blood chemistry: Day 1* sodium, potassium, BUN, glucose, ALT/AST, alkaline phosphatase, total protein, total bilirubin, albumin, creatinine, calcium, chloride and magnesium.
- Azacitidine will be administered daily for 7 consecutive days starting on Day 4 (Days 4 to 10 inclusive). SC preferred but will allow for IV at the discretion of the treating physician. If SC (or IV) is used on Day 4, the other days should follow the same method of administration.
- Pharmacokinetics for azacitidine: Only Cycle 1 Day 4, per Section 8.3.

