8.1.2.6 Reporting of Serious Adverse Events

Adverse events classified as serious require expeditious handling and reporting to Theradex Oncology to comply with regulatory requirements.

All SAEs, regardless of relationship to the study drug, which occur during the period of observation (from the time of eligibility confirmation to 30 days following the date of the last dose of study drug administration) must be immediately reported (within 1 business day of the initial observation of the event) by email, fax or telephone to the Theradex Oncology Safety Desk. Notification by email is preferred. After this period, only those SAEs assessed as possibly, probably or definitely related to the study drug should be reported.

SAEs will be reported to: Theradex Oncology Safety Desk

REDACTED

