9.3.3 Safety Analysis

Safety data will be summarized for the safety population. These data will include adverse events and laboratory parameters. Adverse event terms will be coded using the MedDRA[®], version 21.1 or higher. Adverse events will be summarized by body system, preferred term, severity, and relationship to treatment. Serious adverse events, deaths, and AEs leading to early discontinuation of study drug will be summarized. Laboratory parameters will be summarized by maximum NCI-CTCAE v5.0 severity grade and also by change from pre-treatment to scheduled time points using descriptive statistics. Laboratory parameter listings will include the normal ranges for each parameter. Each value will be classified as falling above, below, or within the normal range.

Data summaries will include only treatment-emergent adverse events (TEAEs), defined as events occurring at the start of infusion on Day 1, Cycle 1 up to and including 30 days after last dose.

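### Section 9.3.3 starts the TEAE window at a Cycle 1 Day 1 infusion that control patients do not receive, and leaves related SAEs beyond 30 days without a planned summary

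*Combined protocol and SAP*

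**What the plan says.** Section 9.3.3 (Safety Analysis) restricts the adverse event output: "Data summaries will include only treatment-emergent adverse events (TEAEs"), which are "defined as events occurring at the start of infusion on Day 1, Cycle 1 up to and including 30 days after last dose". The wording is not split by arm. The same section promises that "Serious adverse events, deaths, and AEs leading to early discontinuation of study drug will be summarized", without giving those summaries a window of their own. Laboratory parameters are handled differently, by maximum grade and "by change from pre-treatment to scheduled time points using descriptive statistics".

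The dosing sections show who receives what on Day 1. Section 6.1 states: "APR-246 treatment (Experimental Arm only) will be administered on Days 1-4". For the control arm, Section 7.4.1 states: "Azacitidine will be administered daily for 7 consecutive days starting on Day 4 (Days 4 to 10 inclusive"). The Synopsis treatment plan gives control azacitidine "on Days 4-10, as a subcutaneous injection or IV infusion, every 28 days", and Section 6.1.2 makes the subcutaneous route the preferred one.

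Sections 8.1 and 8.1.2.1 collect adverse events in both arms from eligibility confirmation to 30 days after the last dose. Section 8.1.2.6 then extends SAE reporting with no end date: "After this period, only those SAEs assessed as possibly, probably or definitely related to the study drug should be reported".

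**The concern.** The safety profile against azacitidine alone is a secondary objective (Section 3.2), and the by-arm adverse event tables are its main output. The rule for what enters those tables should work in both arms and be fixed beforehand, particularly in an open-label trial. This rule names a starting event that one arm does not have, so whoever programs the tables must pick a substitute, and the possible substitutes classify control events on Days 1 to 3 differently.

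At the other end, sites must send in a class of events judged related to treatment, while the analysis section limits adverse event summaries to a window that excludes them. Late related SAEs could be reported by sites and still be absent from the planned safety results.

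**Working it through.** The plan gives no figure for this point. The check is a comparison of the dosing days with the window, followed by day counts.

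**Does the starting event exist in each arm?** In the experimental arm the APR-246 infusion begins on Cycle 1 Day 1, so it does. In the control arm no drug is scheduled on Days 1 to 3, and the first azacitidine dose is on Day 4 by either route. The event is absent even for a control patient given azacitidine intravenously.

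**What can the control start mean?**

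| Reading | Control start | Consequence |
|---|---|---|
| Literal | None | Window undefined |
| Calendar Cycle 1 Day 1 | Day 1 | Days 1 to 3, before any drug, count as treatment-emergent |
| First dose received | Day 4 | Matches exposure, but is not what the text says |

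The choice affects real records, because collection starts at eligibility confirmation. Observation on those days also differs. Experimental patients attend for infusions with vital signs before, during and at the end of each (Section 7.3.1.1). Footnote f to the Schedule of Study Evaluations says control patients need no physical exam or vital signs on each day before their first azacitidine.

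**How large is the calendar-day effect?** Assume that the last azacitidine dose falls on Day 10 of the final 28-day cycle and that there are no delays. For c cycles:

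- Last dose day = 28 × (c − 1) + 10
- Window end = last dose day + 30
- Untreated share of the control window = 3 / window end

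| Cycles (assumed) | Last dose day | Window from Day 1 (days) | Window from Day 4 (days) | Untreated share if Day 1 is used |
|---|---|---|---|---|
| 1 | 10 | 40 | 37 | 3/40 = 7.5% |
| 6 | 150 | 180 | 177 | 3/180 = 1.7% |
| 12 | 318 | 348 | 345 | 3/348 = 0.9% |

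With the planned 77 control patients (Section 9.1), all dosed, this is 77 × 3 = 231 untreated patient-days. After one cycle that is 231 of 77 × 40 = 3,080 patient-days, again 7.5%.

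**How many patients might this touch?** The documents give no adverse event rate, so this is only an illustration. With r onsets per patient per 28 days at a constant rate, the probability of at least one onset in three days is 1 − exp(−3r/28).

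| r (assumed) | Probability | Of 77 control patients |
|---|---|---|
| 0.5 | 5.2% | about 4 |
| 1 | 10.2% | about 8 |
| 2 | 19.3% | about 15 |

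**What happens after 30 days?** The TEAE window and routine collection both close 30 days after the last dose, in both arms. Section 8.1.2.6 continues past that point for related SAEs only. Those events lie outside the TEAE definition, and Section 9.3.3 names no other adverse event summary for them. Their number cannot be estimated from the documents.

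**Two smaller gaps in the same sentence.** It does not say which drug's last dose closes the window, although Section 6.2.1 distinguishes stopping APR-246 or azacitidine from stopping all study treatment. It also has no rule for a pre-existing condition that worsens on treatment.

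**The case against.** The best defence is that the intent is clear and the effect small. The safety population includes anyone given azacitidine, and Section 7.4.1 records control-arm adverse events from Day 1. A reader might infer from the literal definition that the control arm would show no TEAEs at all; no reasonable analyst would produce an empty column. Read as calendar Day 1, both arms start on the same protocol day and close by the same rule, so the text does not establish that the arms are counted differently. What is left is three pre-drug days in Cycle 1. This stands as to size. It does not settle which reading applies.

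A reader might also infer that all safety output stops at 30 days. The documents do not support that. The restriction concerns adverse events; laboratory summaries follow scheduled time points, and Section 8.1.1 tabulates vital signs, ECG and physical exam with no such limit. Nor is it established that late deaths are dropped. Section 9.3.3 lists deaths separately and leaves their window unclear, and overall survival counts every death from randomization (Section 8.2.2). Late related SAEs need not go unseen either, since the IDMC assesses cumulated SAEs with no stated cut-off (Section 8.1.3).

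The 30-day limit matches routine collection, so keeping later events out of the comparative TEAE tables is defensible. That justifies the limit on the TEAE tables but not the absence of any other summary. Section 8.1.1 does tabulate adverse events without naming TEAEs, but this conflicts with the restriction in Section 9.3.3, and the two need reconciling.

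Finally, a separate statistical analysis plan may define TEAEs by arm. Its text is not available here. Section 9.3.1 defers only subgroup analyses to it, and Section 9.3.3 defers nothing.

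**Conclusion.** The point holds in limited form. The TEAE start is wrong as written for the control arm: it is either undefined or, on the calendar reading, takes in three untreated days. That is 7.5% of the window after one cycle, 1.7% after six and 0.9% after twelve, given the assumed cycle numbers and no dose delays. Separately, related SAEs more than 30 days after the last dose must be reported but have no planned AE or SAE summary; how many there would be is unknown.

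The end rule is the same in both arms and adds no asymmetry. No efficacy analysis, sample size, power or alpha is affected. The change is worth making because safety is compared between arms in an open-label trial and the correction is short.

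**What to change.** In Section 9.3.3:

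1. Define a TEAE in both arms as an event that starts or worsens from the patient's first dose of any study drug (APR-246 or azacitidine) to 30 days after the last dose of any study drug.
2. Summarise events between eligibility confirmation and first dose separately.
3. Add a separate summary or listing, by arm, of related SAEs after 30 days and of all deaths regardless of window.
4. Do not merge the late related SAEs into the TEAE counts. They are selected by investigator attribution, which is open to influence when treatment is known.

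The cost is small. The control TEAE window becomes three days shorter than the experimental one (37 against 40 days after one cycle, 177 against 180 after six), all of it in Cycle 1, and there is one additional table or listing. No new patient data are needed: adverse event onset dates, dosing dates, survival status and late related SAEs are already recorded or reportable. Late SAE reports go to the safety desk, so their transfer to the analysis data should be confirmed.

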9.3.4 Pharmacokinetic Analysis

APR-246 concentrations will be determined by a validated high-performance liquid chromatography (HPLC) tandem mass spectrometry (LC/MS/MS) method. A population PK model will be used to estimate individual C_{max} , AUC and CL for each patient. APR-246 AUC and C_{max} will then be tested for association with signs of efficacy and safety. If an observable trend exists, a PK/PD model will be developed to evaluate the exposure-response relationship between APR-246 plasma exposure and outcome measures. Demographic and clinical data (ethnicity, current age, body weight, sex, disease status, etc.) will be utilized to assess interpatient variability in the PK and PK/PD relationships.

Azacitidine concentrations will be determined. The PK parameters will be derived using non-compartmental methods. C_{max} and AUC_{0-4h} will be compared between treatment arms on Day 4 (azacitidine with and without APR-246) to determine the impact of APR-246 on azacitidine PK.

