
Statistics
	
This study will be a multi-center, open-label, randomized, controlled Phase III trial to compare the efficacy of APR-246 in combination with azacitidine versus azacitidine alone for the treatment of TP53 mutant MDS.
 
Analysis Populations
 
Intent-to-treat (ITT): All patients who are randomized on study will be considered eligible for the ITT population and will be used for demographics, baseline characteristics summaries. The ITT population will be the primary analysis population for efficacy.
 
Efficacy evaluable (EE): All patients who complete at least one treatment cycle of APR-246 and azacitidine and who have at least one post-treatment clinical response assessment. Patients who fail to complete one treatment cycle will also be considered EE if they show clear evidence of clinically significant disease progression. The EE population will be the secondary analysis population for efficacy.
 
Safety population: Patients will be evaluable for safety if they receive at least one dose of APR-246 or azacitidine. The safety population will be used to summarize exposure and safety parameters.
 
Pharmacokinetics (PK): Patients will be evaluable for pharmacokinetics if at least one sample for PK evaluation has been obtained.
 
Determination of Sample Size
 
This trial assumes a sample size of 154 patients with 77 patients randomized in a 1:1 ratio to one of the two treatment arms (APR-246 + azacitidine treatment versus

azacitidine treatment alone). If the true CR rate is 50% for the treatment arm and 25% for the control arm, the trial will have 90% power to detect a statistically significant effect in favor of the APR-246 treatment combination at a 2-sided alpha = 0.05 significance level.

Efficacy Analyses

Primary endpoint CR will be summarized for all randomized patients (ITT) as the proportion of patients (%) with CR. CR will be compared between arms using a Cochran-Mantel-Haenszel (CMH) test stratified by age (< 65 years versus ≥ 65 years). In addition to presenting the CR rate and associated exact 95% confidence intervals (CI) for each treatment arm, the treatment effect will be described using the CMH estimate of the common odds ratio together with its associated 95% CI.

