2.4 Azacitidine

Azacitidine is a nucleoside metabolic inhibitor indicated by the U.S. FDA for the treatment of patients with the following French-American-British (FAB) MDS subtypes: refractory anemia (RA) or refractory anemia with ringed sideroblasts (if accompanied by neutropenia

or thrombocytopenia or requiring transfusions), refractory anemia with excess blasts (RAEB), refractory anemia with excess blasts in transformation (RAEB-T), and chronic myelomonocytic leukemia (CMML). The recommended starting dose for the first treatment cycle, for all patients regardless of baseline hematology laboratory values, is 75 mg/m² subcutaneously or intravenously, daily for 7 days. Patients are to be premedicated for nausea and vomiting. Repeat cycles every 28 days. Treatment may be continued as long as the patient continues to benefit.

Azacitidine is rapidly absorbed after subcutaneous or IV administration with a V_d of 76 ± 26 L and a half-life of 41 ± 8 minutes. C_{max} is reached after about 30 minutes. Azacitidine and its metabolites are known to be substantially excreted by the kidney, and the risk of adverse reactions to this drug may be greater in patients with impaired renal function. Urinary excretion is the primary route of elimination; the cumulated urinary excretion is 85% of radioactive dose with less than 1% recovered in feces over 3 days.

Azacitidine undergoes spontaneous hydrolysis in aqueous solution and is deaminated by cytidine deamidases, whereas APR-246 is glucuronidated. Although both compounds and their degradation products and metabolites are primarily eliminated by urinary excretion drug-drug interaction is not likely, but will be investigated as part of the current trial.

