4.4.2 Azacitidine

Chemical Name: 4-amino-1-β-D-ribofuranosyl-s-triazin-2(1H)-one

Formulation, preparation, storage and stability: Please see commercial package insert approved by regulatory agencies ^{30,31}

Route of Administration: Subcutaneous injection preferred*; or intravenous infusion.

Azacitidine is administered SC or IV for 7 consecutive days (Days **4-10**).

* SC preferred but will allow for IV at the Investigator's discretion. However, the same route should be maintained over the 7-day treatment period (whichever route is used on Day **4**, the other days should follow the same route of administration).

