6.1.1 Experimental Arm (APR-246 + Azacitidine)

APR-246 will be administered as a 6-hour intravenous infusion daily on days 1-4 of each 28-day cycle. APR-246 fixed dose is 4.5 g. APR-246 is administered in a 2-step infusion:

Step 1: Loading dose of 1.5 g for the first 45 minutes (± 2 min)

Step 2: Maintenance dose of 3 g over 5 hours 15 minutes (± 30 min)

Detailed instructions on vial concentration, preparation and dispensing can be found in the Pharmacy Binder. The infusion timing, including start/stop times and the time of rate change, must be recorded.

Azacitidine will be given at the standard dose of 75 mg/m² SC or IV over 7 consecutive days, Days **4-10**. On **Day 4** azacitidine is administered immediately after the APR-246 infusion. SC method is preferred but IV is allowed at the Investigator's discretion. However, the same route should be maintained over the 7-day treatment period (whichever route is used on Day **4**, the other days should follow the same route of administration). Detailed instructions on preparation and administration can be found in the Pharmacy Binder, current package insert, and in Section 6.1.2, below.

[figure not shown]

Figure 4. Drug Administration Schema for Experimental Arm: APR-246 and Azacitidine

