6.1.2 Control Arm (Azacitidine Only)

Azacitidine will be given at the standard dose of 75 mg/m² SC or IV over 7 consecutive days, Days **4-10**, every 28 days. SC method is preferred but IV is allowed at the Investigator's discretion. However, the same route should be maintained over the 7-day treatment period (whichever route is used on Day 4, the other days should follow the same route of administration).

Detailed instructions on preparation and administration can be found in the Pharmacy Binder, and current package insert.

Control Arm: Azacitidine only

[figure not shown]

Figure 5. Drug Administration Schema for Control Arm: Azacitidine Only

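### The azacitidine interaction comparison takes no account of SC or IV route, so the Cmax ratio between arms can be shifted or blurred by route

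*Combined protocol and SAP*

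**What the plan says.** Section 2.4 says of azacitidine and APR-246 that "drug-drug interaction is not likely, but will be investigated as part of the current trial". Section 9.3.4 is where this is done. For azacitidine, "The PK parameters will be derived using non-compartmental methods", and Cmax and AUC0-4h "will be compared between treatment arms on Day 4" in order "to determine the impact of APR-246 on azacitidine PK". Section 8.3 limits azacitidine sampling to selected sites, in Cycle 1 on Day 4, and gives no number of patients. Table 9 applies one set of sampling times to everyone, counted from the end of administration.

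On route, Sections 6.1.1 and 6.1.2 use the same words for the two arms: "SC method is preferred but IV is allowed at the Investigator's discretion". Section 4.4.2 adds that "the same route should be maintained over the 7-day treatment period", which fixes route within a patient's course but not across patients or arms. The synopsis describes a "multi-center, open-label, randomized, controlled Phase III trial", and Section 7.2.2 stratifies randomization by age group alone.

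Neither Section 8.3, Section 9.3.4 nor the PK paragraph of the synopsis splits, adjusts or restricts the azacitidine analysis by route. The one sentence on covariates in Section 9.3.4 belongs to the APR-246 population model, and route is not among the covariates it names.

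**The concern.** An IV infusion and an SC injection of the same dose give different concentration profiles, and above all different peaks. If the two routes are mixed within each arm, the ratio of Cmax between arms contains a route component whenever the IV share differs between arms. Section 9.3.4 would read that component as an effect of APR-246, or the component could mask a real effect. If the shares are equal there is no bias, but the mixture of routes adds variance and widens the interval.

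This is the only planned comparison of azacitidine exposure with and without APR-246. It uses a single occasion at selected sites, so an ambiguous result could not be checked elsewhere in the trial. It serves a secondary PK objective. The primary comparison of complete remission rates is not affected.

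**Working it through.** The plan gives no sample size, expected ratio, equivalence bounds or power for this comparison, so there is no stated figure to reproduce. The check asks how far route alone can move the result.

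**Inputs from the protocol.** Section 2.4: half-life 41 ± 8 minutes, and peak at about 30 minutes (used here for SC). Table 9: samples before dosing, at the end of administration, and 0.25, 0.5, 1, 2 and 4 hours afterwards.

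**Assumed, because not given.** Infusion length T of 10 to 40 minutes; SC bioavailability F of 0.8 to 1.0; one compartment; IV share; size of the PK subset; within-route log SD s of 0.4 to 0.6.

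**Step 1: IV/SC ratio R for Cmax.** Let k = ln 2 / half-life. Per unit of dose/volume, the SC peak is F·exp(−k·tmax), and the IV peak, at the end of infusion, is (1 − exp(−kT))/(kT). Volume cancels in the ratio. At 41 minutes k = 1.014 per hour, so at F = 1 the SC peak is exp(−0.507) = 0.602.

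- T = 10 min: IV peak 0.920, R = 0.920/0.602 = 1.53.
- T = 40 min: IV peak 0.727, R = 0.727/0.602 = 1.21.

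Over half-lives of 33 to 49 minutes:

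| Half-life (min) | T (min) | R, F = 1.0 | R, F = 0.9 | R, F = 0.8 |
|---|---|---|---|---|
| 33 | 10 | 1.69 | 1.88 | 2.12 |
| 33 | 40 | 1.27 | 1.41 | 1.59 |
| 41 | 10 | 1.53 | 1.70 | 1.91 |
| 41 | 40 | 1.21 | 1.34 | 1.51 |
| 49 | 10 | 1.43 | 1.58 | 1.78 |
| 49 | 40 | 1.17 | 1.30 | 1.46 |

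So R is about 1.2 to 1.7 at F = 1, and reaches about 2.1 at F = 0.8.

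**Step 2: the same ratio for AUC.** The trapezoidal rule at the Table 9 times gives 0.97 to 1.03 at F = 1, 1.07 to 1.14 at F = 0.9, and 1.21 to 1.28 at F = 0.8. A route effect on AUC of any size therefore needs incomplete SC bioavailability.

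**Step 3: spurious ratio between arms.** With no true interaction, the geometric mean ratio is R^d, where d is the IV share in the experimental arm minus that in the control arm. At d = 0.20:

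- 1.2^0.20 = 1.04
- 1.7^0.20 = 1.11
- 2.1^0.20 = 1.16

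**Step 4: can d be that large by chance?** With an assumed IV share of 30% in both arms, the 95% range of d is ±1.96·√(2·0.3·0.7/n). That is ±0.40 at n = 10 per arm and ±0.28 at n = 20 per arm. In subsets of that size, a 20-point difference needs no difference in prescribing.

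**Step 5: loss of precision with equal shares.** Mixing routes adds p(1 − p)·(ln R)² to the log variance, where p is the IV share. The width of the interval relative to a route-adjusted one is √(s² + p(1 − p)(ln R)²)/s. At p = 0.5:

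- R = 1.2, s = 0.6: √(0.36 + 0.25·0.0332)/0.6 = 1.01
- R = 1.7, s = 0.4: √(0.16 + 0.25·0.2816)/0.4 = 1.20
- R = 2.1, s = 0.4: √(0.16 + 0.25·0.5505)/0.4 = 1.36

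Half IV is the least favorable share. At p = 0.3 the last figure becomes √(0.16 + 0.21·0.5505)/0.4 = 1.31.

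**Step 6: after the change.** When patients are compared within route, or with route in the model, R drops out and the spurious ratio is 1.00 for any d.

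**The case against.** The best defense is that the protocol does not say the routes are pooled. It names no test or model, the synopsis promises only descriptive statistics for PK, and nothing forbids summaries by route. Section 9.3.1 refers to a separate Statistical Analysis Plan and Section 8.3 to a Laboratory Manual. Neither text is available here, and either could contain a route rule. This stands as a limit on certainty. It does not remove the gap: a comparison of arms with no mention of route is, as written, a comparison of mixed routes.

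It is also fair to say that SC is preferred in both arms in identical words, that an interaction is called unlikely, and that azacitidine PK falls under the last of nine secondary objectives. These points limit the importance of the matter, but the remedy costs very little.

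A reader might infer several stronger things that the documents do not support:

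- **IV will be used more often in the experimental arm.** Those patients have just had a 6-hour infusion on Day 4, so this is plausible, but no section says so. Nor does any section say whether route is chosen before or after randomization.
- **IV peaks are three or four times SC peaks, or the interval doubles in width.** The protocol's half-life and time to peak, with the infusion lengths and bioavailability assumed above, do not reach such values.
- **AUC0-4h is distorted to a similar degree.** At full SC bioavailability it is not.
- **Route is already recorded.** Vital-sign timing depends on route, so sites will know it, but no section lists it as a data item.

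**Conclusion.** The point holds for Cmax, at modest size. As written, the comparison can attribute a route difference to APR-246. The spurious Cmax ratio is about 1.04 to 1.16 for a 20-point difference in IV share, whether that arises by chance or by choice. With equal shares there is no systematic bias, only an interval about 1.01 to 1.36 times as wide when half the patients receive IV. For AUC0-4h the route effect is within about 3% at full SC bioavailability, and matters only if bioavailability is lower.

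These figures rest on a one-compartment model, the 30-minute peak applied to SC, and the assumed infusion length, bioavailability, IV shares and within-route SD. The number of patients sampled is not stated, so the chance-imbalance figures are illustrations. This is a free improvement to a secondary analysis.

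**What to change.** In Section 9.3.4, state that log Cmax and log AUC0-4h of azacitidine will be compared between arms with route of administration (SC or IV) as a factor, or within route, and that both parameters will be summarized by arm and route. Confirm that the route used on Cycle 1 Day 4 is captured in the PK data set. If the Laboratory Manual or the separate Statistical Analysis Plan already contains such a rule, a cross-reference is enough.

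The cost is a sentence or two of text, one model term and, if route is not yet captured, one data field. The by-route groups may be small, and their summaries should be read accordingly. The way azacitidine is given does not change.
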